Related: This relationship suggests that a reasonable temporal sequence of the event with device administration exists and, based upon known or previously reported adverse reactions to the device or class of devices or judgment based on the Investigator's clinical experience, the association of the event with the study device seems likely.

The severity (intensity) of AE will be graded according to the following definitions:

Mild: The subject experiences awareness of symptoms but these are easily tolerated or managed without specific treatment.

Moderate: The subject experiences enough discomfort to cause interference with usual activity, and/or the condition requires specific treatment.

Severe: The subject is incapacitated with inability to work or do usual activity and/or the event requires significant treatment measures.

An unexpected AE is one that is not consistent with the subject's past medical or acute burn history and is not evident from previous clinical experience with the test product or reasonably anticipated from pre-clinical information. An AE will be classified as 'serious' when it refers to any event during the 12-month study period that results in any of the following:

- Death
- Life-threatening adverse experience (i.e., the subject was at immediate risk of death from the reaction as it occurred)

- Inpatient hospitalization or prolongation of existing hospitalization
- Persistent or significant disability or incapacity
- A medically significant event or one requiring intervention to prevent one of the outcomes listed above and suspected to be due to the test product

All SAE will be followed until stabilization or improvement.

Clinical site personnel will be trained to follow study processes for reporting SAE. SAE reports will be managed by the clinical research team. The Principal Investigator will manage the process of ensuring that reports are completed appropriately and forwarded in a timely manner to all required recipients. The Principal Investigator will also assess individual and accumulating SAEs, AEs, and other safety data on a regular basis to identify any safety signals that should be brought to the attention of the Sponsor, , IRB offices, and/or the FDA.

Reporting for SAE which **are expected and not related** to KeraStat Gel will be as follows:

- The Principal Investigator (PI) will be notified within 24 hours of the Investigator becoming aware of any SAE that is expected or not related to the test product.
- The PI will promptly notify the Sponsor, the local IRB office and the central IRB office of all SAE.
- The Investigator will complete an SAE form and send it to all IRB offices and Sponsor within ten days of the SAE.

Reporting for an SAE that is determined to be **both unexpected and deemed related** to KeraStat Gel treatment will be as follows:

- SAE that are both unexpected and possibly or probably related to the test product will be reported within 24 hours of the Investigator becoming aware of the event via telephone, facsimile, or e-mail to the PI.
- The PI will notify the Sponsor, the local IRB office, and the central IRB office of all SAE within 72 hours of learning of the SAE.
- The Investigator will send the SAE report to all IRB offices and Sponsor within ten days of the SAE.
- The Sponsor will submit the SAE report to all Investigators and will submit the FDA MedWatch report to the FDA.
 - Within 7 calendar days for fatal or life-threatening SAE
 - Within 15 calendar days for all other unexpected and related SAE

Any unanticipated problems involving risks to subjects or others and AEs shall be promptly reported to the IRB, according to institutional policy. Reporting to the IRB is required regardless of the funding source, study Sponsor, or whether the event involves an investigational or marketed drug, biologic or device. Reportable events are not limited to physical injury, but include psychological, economic and social harm. Reportable events may arise as a result of drugs, biological agents, devices, procedures or other interventions, or as a result of questionnaires, surveys, observations or other interactions with research subjects.

All members of the research team are responsible for the appropriate reporting to the IRB and other applicable parties of unanticipated problems involving risk to subjects or others. The PI, however, is ultimately responsible for ensuring the prompt reporting of unanticipated problems involving risk to subjects or others to the IRB. The PI is also responsible for ensuring that all reported unanticipated risks to subjects and others that they receive are reviewed to determine whether the report represents a change in the risks and/or benefits to study subjects, and whether any changes in the informed consent, protocol or other study-related documents are required.

In order to ensure the safety, rights or welfare of research subjects any event, incident, experience, or outcome that alters the risk versus potential benefit of the research will prompt a substantive change in the research protocol or informed consent process/document.

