⁷ Bloemen, M.C.T., et al., Prevention and curative management of hypertrophic scar formation. *Burns*, 2009. 35(4): p. 463-475.

Protocol version: 5

Template updated 5 Jul 2021

Methods and Measures

Design

This study is a randomized, controlled, within-subject trial examining the effectiveness of KeraStat Gel, as compared to the institutional SOC, Mepilex Ag, in improving wound cosmesis. Once the Investigator has determined the subject is a candidate for inclusion in the study, the subject will be approached about enrolling in this study. A total of 30 burn subjects presenting to the Burn Centers will be enrolled.

Upon presenting to the hospital, potential study subjects will be assessed for inclusion and approached for consent, as appropriate. Once the subject and/or legal guardian has consented to participate in the study, baseline assessments can be completed. We anticipate that the majority of subjects presenting with burns that qualify for inclusion in the study will have at least one night stay in the hospital; however, this is not criteria for inclusion. KeraStat Gel and Mepilex Ag will each be randomized to application on one of two identified burn sites on the subject, Burn A or Burn B. All subjects will have one burned area dressed with KeraStat Gel and a second area dressed with Mepilex Ag per SOC. The Investigator or study staff will initially apply the dressings per a computer-generated randomization scheme. The burn dressed with KeraStat Gel will have a secondary dressing of petrolatum gauze and telfa. For subjects who have more than two burns, all additional burns will be treated according to the physician's discretion. Subjects will be provided with enough KeraStat Gel and KeraStat Gel-related dressing supplies upon hospital discharge to accommodate prescribed dressing changes until their next visit. The Investigator will instruct subjects on dressing changes as required by institutional SOC guidelines and instructions for use of KeraStat Gel prior to discharge. The need to maintain treatment consistency will be stressed; Burn A and Burn B should always receive their designated dressing.

For the first 4 weeks, subjects will have weekly visits with site staff. On days 7 and 21, this visit will be remote. On days 14, and 28, this visit will be an office visit.

[figure not shown]

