Below is a schematic overview of the study.

Optional at-home questionnaire and photographs at virtual visits on weeks 1 and 3

Wound assessments, questionnaires, photographs, TEWL assessment at 3 months, 6 months, 1 year

Setting

This study will be conducted in the Wake Forest (WF) Burn Center and in the University Medical Center New Orleans (UMC). Subjects may continue treatment as inpatients or as outpatients.

Subjects Selection Criteria

- **Inclusion Criteria**

- Males and females, age 6 years and older
- Written informed consent and assent, if applicable (including parent if subject is a minor)
- Presenting with at least two comparable, discrete, and separate partial thickness thermal burns, as determined by the Investigator, measuring 50-1,000 cm² each
- Study wounds identified are partial thickness depth
- KeraStat Gel and Mepilex Ag can be applied to the randomized study burn wounds as definitive care treatment within 72 hours from time of injury
- Overall total body surface area (TBSA) burned < 20%

- **Exclusion Criteria**

- Pregnant or nursing
- Prisoner
- Presence of inhalation injury, as determined by the Investigator
- Injury requiring formal intravenous fluid resuscitation
- Concomitant non-thermal traumatic injuries
- Chronic medical conditions including, but not limited to, documented > renal impairment (Cr > 2.5 mg/dL), hepatic impairment (Total bilirubin > 2.5 mg/dL), thromboembolic disorders, active infection in study wound areas, uncontrolled diabetes (HbA1C > 7%), HIV infection, history of melanoma or systemic malignancy within the last 10 years
- Receiving corticosteroids, immunosuppressive agents, radiation or chemotherapy, topical growth factors, or any other medication the Investigator feels will affect wound healing
- Not expected to live at least 13 months post-burn
- Previously treated with a skin graft at either of the treatment sites

- Chemical or electrical burn
- Proposed study wounds are full thickness
- Any condition the Investigator determines will compromise subject safety or prevent the subject from completing the study

- **Sample Size**
The study size is 30 subjects, two wounds per subject, 30 wounds per treatment cohort resulting in 60 total wounds.

Because this trial is designed to examine long-term outcomes, no interim analyses or stopping rules are planned.

Interventions and Interactions

Intervention: KeraStat Gel

Agent description

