At baseline, demographic and medical history will be collected, and inclusion/exclusion criteria will be confirmed. If the subject meets these criteria, vital signs will be collected, and the wounds will be randomized to treatment including KeraStat Gel dressings or SOC. Two burns identified by the Investigator will be labeled Burn A and Burn B by study staff and noted on the Case Report Form (CRF). The randomization scheme will be generated in nQuery Advisor 7.0 in advance by the study statistician. An adequate, sequentially numbered, opaque, sealed envelope set will be produced prior to the implementation of the protocol for the site to use. These envelopes will be shipped and maintained at the site with the trial staff member designated by the Investigator or the Investigator themselves to conduct randomization. The staff will choose the first envelope in sequence, record the subject ID and date of the randomization on the outside of the envelope. They will open the envelope and reveal the index card with the treatment assignment for Burn A and Burn B, record again the Subject ID and randomization date on that card, and then upload a photo of the completed card with the Subject's source documentation for the clinic visit. No subject may be randomized early into the study. All envelopes at each site must be used in sequential order. Any alterations to this procedure will be considered a protocol violation. Burns will be examined and photographed. The subject will be asked to complete the Visual Analog Scale (VAS) pain score for each burn site on study. Once each treatment is applied, the subject will once again complete the VAS pain score for each burn site. Thus, two VAS pain scores will be collected for each burn at each treatment application by study staff.

Hospital staff will change dressings until the subject is discharged from the hospital. At discharge, the burns will once again be examined and photographed. The subject will be asked

Protocol version: 5

Template updated 5 Jul 2021

to complete the Visual Analog Scale (VAS) pain score for each burn site on study. Once each treatment is applied, the subject will once again complete the VAS pain score for each burn site. Subjects will be provided with enough KeraStat Gel-related dressings to last 17 days. Subjects will be instructed on dressing changing procedures for both burns per institutional SOC guidelines.

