Dressings will be changed per institutional SOC guidelines but at a minimum of every 3 days. Subjects will return to the clinic on days 14 ± 3 and 28 ± 3 post-enrollment for the first 4 weeks and at months 3 (± 7 days), 6 (± 7 days), and 12 (± 14 days) post-enrollment. Subjects will also participate in a remote visit on days 7 ± 3 and 21 ± 3 post-enrollment. Dressing changes will be continued until reepithelialization is achieved. During each visit, study staff will document the number of dressing changes that occurred outside of clinic visits as well as any pertinent information related to the dressing changes. During visits when dressing changes are still necessary, subjects will complete the VAS pain score before and after dressing changes to each burn, and any unanticipated adverse events related to the device will be logged. Subjects who are able and willing will download an application on their smartphone that will prompt them to record the VAS pain score before and after dressing changes will complete this during remote visits on days 7 and 14. Subjects will also be asked to upload photos of the burns at days 7 and 21 utilizing the medical center's MyChart application. Appearance of the sites will be assessed at months 3, 6, and 12 using the POSAS. During the visits at 3, 6, and 12 months, sites will be subjected to 3 measurements of TEWL. Photographs will be obtained at all in-person visits and may be subjected to wound closure and percent epithelialization measurements via ImageJ. Recording of adverse events (AE), measurement of vital signs, examination of the wound/site of wound, and notation of concomitant medication and procedures will also take place during each visit. All measures will be completed if an individual agrees to a final visit after withdrawal from the study.

Masking

This study will be an open-label study.

Schedule of Events

Baseline Testing (All subjects)

- Photographs (prior to start of treatment)
- Vital signs (e.g., blood pressure, heart rate, temperature, height, weight)
- Examination of wound, including wound measurement
- Concomitant medications
- VAS pain score before and after dressing application

Discharge

- Adverse events

- Vital signs
- Examination of wound, including wound measurement and percent reepithelialization
- Photography of treatment site
- Concomitant medications and procedures
- Dressing change
- VAS pain score before and after dressing change

Day 7, 21 (± 3 , Remote visit)

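### The order of the two dressing changes at pain-scored sessions is left open in an open-label, within-subject trial; doing Burn A first would randomize it at almost no cost (secondary pain endpoint only)

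*Combined protocol and SAP*

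**What the plan says.** The Design section places both treatments on the same person: "All subjects will have one burned area dressed with KeraStat Gel and a second area dressed with Mepilex Ag per SOC". Under Interactions, the envelope is opened to "reveal the index card with the treatment assignment for Burn A and Burn B". What is randomized is therefore which dressing goes on which labelled burn; the card is not said to carry a sequence.

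Pain scoring is described in two ways, both under Interactions:

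- At baseline and discharge the subject scores each burn, the treatments are applied, and then: "Once each treatment is applied, the subject will once again complete the VAS pain score for each burn site". For the baseline session the section adds: "Thus, two VAS pain scores will be collected for each burn at each treatment application by study staff".
- At later visits where dressings are still needed, "subjects will complete the VAS pain score before and after dressing changes to each burn".

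Neither description says which burn is changed first, how long to wait between burns, or whether the first burn is re-scored before the second is touched. The Schedule of Events and the assessment table have no entry for order. The Masking section makes the study open label. Pain at dressing changes is a named secondary objective. For it, the Analytical Plan gives box plots by treatment group over time and a Kruskal-Wallis test across time, with no paired test and no order term. The same section leaves a separate SAP to be finalized before database lock.

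**The concern.** Randomizing dressing to burn protects the pain comparison against differences between the two burns. It does not protect against a sequence chosen after the dressing on each burn is known. Two procedures done close together in one person can affect each other's scores, and how they do so depends on how the scoring instructions are read:

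- **Both after scores taken once both dressings are on** (one reading of the baseline and discharge text). The first burn has had longer to settle, but its score also follows a second procedure elsewhere on the body.
- **Each burn scored before and after its own change** (a reading the later-visit text allows). The second burn's before score, and possibly its after score, can carry pain or distress from the first change.

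The direction may differ, but order can matter under either reading. If one dressing is usually changed first, any order effect is confounded with the dressing effect in the between-dressing VAS contrast. That bias would not shrink with more subjects or more visits. If the order was not recorded, the analysis could not adjust for it.

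**Working it through.** **Figures in the plan.** The Sample Size entry reads: "The study size is 30 subjects, two wounds per subject, 30 wounds per treatment cohort resulting in 60 total wounds". The count agrees (30 × 2 = 60). No alpha, power, effect size or standard deviation is given, and nothing ties the number to pain, so there is no planned pain figure to reproduce. Two scores per burn make 2 × 2 = 4 scores per subject at a session where both burns are dressed. The VAS runs from 0 to 10 cm.

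**Assumed inputs (none is in the documents).**
- e: amount in cm by which the after-change score of the burn done second exceeds that of the burn done first, apart from any dressing effect. It could be negative.
- q: share of sessions in which one given dressing is changed first.

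**Bias in a raw after-change score.** The other dressing is raised by e in a share q of sessions and lowered by e, relatively, in the remaining 1 - q:

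bias = qe - (1 - q)e = (2q - 1)e

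| q | e = 0.5 cm | e = 1.0 cm | e = 1.5 cm |
|---|---|---|---|
| 0.5 | 0 | 0 | 0 |
| 0.7 | 0.4 × 0.5 = 0.2 | 0.4 × 1.0 = 0.4 | 0.4 × 1.5 = 0.6 |
| 0.9 | 0.8 × 0.5 = 0.4 | 0.8 × 1.0 = 0.8 | 0.8 × 1.5 = 1.2 |

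**Consequence for a paired test.** The plan specifies no paired test, so this is for scale only. Take 30 subjects, one paired difference each, q as a share of subjects, no true dressing difference, two-sided 5% level, and an assumed SD of the within-subject difference (sd) of 1.5 to 2.5 cm. The variance of the difference is sd² + 4e²q(1 - q).

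Example with sd = 2.0, e = 1.0, q = 0.9:
- Variance = 4 + 4 × 1 × 0.9 × 0.1 = 4.36, so SD = 2.09.
- Standard error = 2.09/√30 = 0.38, and bias/SE = 0.8/0.38 = 2.1.
- Rejection rate by normal approximation is about 56% (52% in a simulated paired t-test).

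Over e = 0.5 to 1.0 cm and sd = 1.5 to 2.5 cm:
- q = 0.7: false-positive rate 7% to 24%.
- q = 0.9: 14% to 77%.
- q = 0.5: 5% (simulated 4.8% to 5.2%).

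The difference detectable with 80% power is (1.96 + 0.84) × sd/√30, or 0.77 to 1.28 cm. A strongly habitual order could therefore create or hide an effect approaching that size.

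**If Burn A is always changed first.** Dressing is randomized to A and B, so the expected value of 2q - 1 is zero, and so is the expected bias. Chance imbalance remains. Under simple 1:1 assignment (an assumption, since the documents do not say whether the scheme is blocked), its standard error is e/√30 = 0.18e. A split of 20:10 or worse would occur in 9.9% of trials of 30. An order term in the analysis deals with this.

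**The case against.** The strongest reply is that the protocol permits a dressing-linked order but does not cause one. Without carry-over, or with an order unrelated to dressing, nothing is biased. That stands, and it limits the point to a conditional one.

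Several stronger readings are tempting but not supported:

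- **That a habitual order is likely because the gel is more laborious to change.** Agent Administration describes soap-and-water removal of the gel, with gauze wiping as needed. No section describes how Mepilex Ag is removed, so the contrast cannot be drawn. A habitual order is possible, no more.
- **That pain from the first change necessarily inflates the second burn's score.** Where both after scores follow both applications, it is the first burn's score that has the longer delay and the intervening procedure. The direction is not settled.
- **That every pain analysis would be biased.** If carry-over raised the second burn's before and after scores equally, an after-minus-before comparison would cancel it. The Analytical Plan does not say whether raw or change scores will be used, so the formula above is confined to raw after-change scores.
- **That the problem affects every session, including at home.** Same-session changes are clear at baseline and discharge and implied at days 14 and 28. They are not stated for home scoring, which is optional. Scoring also falls away as burns heal: closure is expected within 21 days for burns not needing grafting.
- **That order is certainly lost.** The CRF is not among the documents, and staff are asked to note relevant details of changes made outside the clinic. The protocol does not ask for order, but that does not prove it goes unrecorded.

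A remedy could also do harm. Finishing Burn A completely before taking Burn B's before score would place that baseline after a potentially painful procedure. The fix below avoids this.

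**Conclusion.** The point holds as a cheap improvement to a secondary endpoint. Order is not fixed, not randomized and not requested in the protocol, while the dressings are known. If order tends to follow dressing and an order effect exists, the raw after-change VAS contrast is biased by (2q - 1)e: 0.2 to 1.2 cm over q = 0.7 to 0.9 and e = 0.5 to 1.5 cm, and zero when order is unrelated to dressing. Both q and e are assumptions. The documents give no carry-over data and no information on customary order, and the upper end combines two high values. A reader might infer that the pain comparison is already invalid; the documents do not show that. POSAS and transepidermal water loss, measured at months 3 to 12, do not depend on the order of dressing changes in this way. The change is worth making because it removes the expected order bias by using the randomization already in place, and it has to be made before the scores are collected.

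**What to change.** In both pain-scoring descriptions under Interactions, and in the app instructions for occasions when both burns are changed together, state the sequence for scored sessions:

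1. Take the before score for both burns before either dressing is touched.
2. Change Burn A, then take its after score.
3. Change Burn B, then take its after score.

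Record the actual order on the CRF, and allow departures where staff judge them necessary, also recorded. Because the envelope assigns the dressings to A and B, this randomizes order with no new envelopes or procedure.

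In the SAP still to be finalized, specify a within-subject comparison of pain between dressings with an order (A/B) term, and say whether it uses raw after scores or change from the before score. The current Analytical Plan has no paired comparison to which the term could be added.

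The cost is a short addition to the protocol and app instructions, one CRF field, and the loss of free choice of order at scored sessions except for recorded departures. Which dressing is used, how often it is changed and how wounds are cared for are untouched.
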